2.5. CLINICAL RISKS/BENEFITS

IPF is a chronic and progressive lethal lung disease for which two treatments (pirfenidone and nintedanib) are currently approved in the EU and US. These treatments appear to slow disease progression but are frequently associated with side effects potentially limiting the use in clinical practice. There thus remains a significant unmet medical need for the investigation and development of novel IPF treatments targeting disease-relevant pathways.

GLPG1690 is the first ATX inhibitor in clinical development for the oral treatment of IPF.

As with any new compound in early development, no benefit can be expected for the individual subjects and safety is paramount. The subjects therefore need to be closely monitored by repeated assessment of clinical and vital signs, ECG, and laboratory safety parameters.

GLPG1690 has been evaluated in a phase I FIH study whereby the administration of single (up to 1500 mg) and multiple ascending oral doses of GLPG1690 (up to 1000 mg *q.d.* for 14 days) in healthy male subjects was considered safe and well tolerated. All TEAEs, the most common ones being headache and diarrhea were at most moderate in severity and transient in nature. No clinically relevant abnormalities related to laboratory parameters, ECG, vital signs, or physical examination were reported.

As there is limited clinical experience with GLPG1690 so far, the study drug should not be administered to subjects with moderate to severe renal impairment, hepatic impairment (Child-Pugh B or Child-Pugh C), or pediatric subjects. The study drug may be administered to elderly subjects. Based on available pre-clinical data, the impact of aging on the elimination of GLPG1690 should not be significant. The hepatic clearance is predicted to be low suggesting GLPG1690 undergoes low metabolism in humans. In terms of renal elimination, < 2% of GLPG1690 is excreted unchanged in urine. Consequently, the fecal route is likely the main route of elimination with secretion of GLPG1690 and potential metabolites via the bile into the feces.

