4. INVESTIGATIONAL PLAN

4.1. OVERALL STUDY DESIGN

This study is a randomized, double-blind, parallel group, placebo-controlled, multicenter, exploratory phase IIa study to evaluate the safety, tolerability, PK, and PD of GLPG1690 in subjects with IPF. In addition, several exploratory assessments will be performed. Male and female subjects of non-child-bearing potential with a confirmed diagnosis of IPF aged 40 years or older will be screened to determine eligibility as per the inclusion and exclusion criteria (see Section 4.2.2 and 4.2.3, respectively). The screening period will be up to 4 weeks.

Written informed consent must be obtained before any study-related procedures take place. During the screening period, following signing of the informed consent form (ICF), the subject's historical HRCT and surgical lung biopsy (SLB; if available) will be sent to central review for the confirmation of the IPF diagnosis through a:

- central review of the chest HRCT
- central review of the SLB (if available)

Note that both the chest HRCT and SLB need to be sent to central review at least 8 days prior to the baseline visit to allow for central reading and confirmation of IPF diagnosis. Additional details are provided in Appendix 2.

At baseline, after the subject's eligibility for the study has been confirmed, subjects will be randomized in a 3:1 ratio to GLPG1690 600 mg *q.d.* or matching placebo administered for 12 weeks.

The subjects will visit the clinical study center at screening (Day-28 to Day -4), Day -1 (baseline), Week 1 (Day 7), Week 2 (Day 14), Week 4 (Day 28), Week 8 (Day 56), and Week 12 (Day 84) or the early discontinuation visit (EDV). In addition, a follow-up visit will be planned 2 weeks after the last administration of study drug (Week 98 [Day 98]). Each subject will be in the study for up to approximately 18 weeks (from screening to follow-up). The end of the study (EOS) will be defined as the last contact with the last subject in the study.

The assessments performed at each visit are detailed in the study flow chart (Section 1).

To enhance the safety and integrity of the study data, an independent medical safety review will be implemented. (See Section 7 for additional information).

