4.2.2. Inclusion Criteria

Subjects who meet all of the following criteria are eligible for the study:

1. Subjects who are able and willing to sign the ICF as approved by the independent ethics committee (IEC).
2. Male or female subjects of non-child-bearing potential aged ≥ 40 years on the day of signing the ICF.
Note: Female subjects will be considered of non-childbearing potential if they are either sterilized, ovariectomized, hysterectomized, or postmenopausal (*i.e.*, at least 24 months of amenorrhea in the absence of other biological or physiological causes [in case of doubt, the subject's follicle stimulating hormone [FSH] levels will be determined and the subject will be considered postmenopausal if the FSH level is ≥ 35 mIU/mL]).
3. Subjects with a chest HRCT performed within 12 months prior to screening visit.
4. Subjects with IPF diagnosed by a multidisciplinary team and confirmed by central review of the subject's HRCT pattern and SLB (if available) (see Appendix 2 for additional details).
5. Subjects meeting all of the following criteria:
 - a. FVC $\geq 50\%$ predicted of normal
 - b. Diffusing capacity for the lungs for carbon monoxide (DLCO) $\geq 30\%$ predicted of normal (corrected for hemoglobin) (see Appendix 3 for additional details).
6. Subjects with a forced expiratory volume in 1 second (FEV₁)/FVC (Tiffeneau-Pinelli index) ratio ≥ 0.70 (based on pre-bronchodilator spirometry).
7. Subjects who are on stable supportive care (*e.g.*, supplemental oxygen, pulmonary rehabilitation) for at least 3 weeks prior to screening and during screening period.
8. Subjects must be in a stable condition and acceptable for study participation based upon the results of a medical history, physical examination, vital signs, 12-lead ECG, and laboratory evaluation.
9. Subjects must have an estimated minimum life expectancy of 12 months in the opinion of the investigator.
10. Male subjects and their female partners must use a highly effective method of birth control. Additional details on these methods are provided in Section 4.2.4.
11. Subjects who are able to understand the importance of adherence to study treatment, study procedures and requirements, including the concomitant medication restrictions.

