4.2.3. Exclusion Criteria

Subjects meeting one or more of the following criteria cannot be selected for this study:

1. Subjects with a known hypersensitivity to any of the study drug ingredients or a history of a significant allergic reaction to any drug as determined by the investigator (*e.g.*, anaphylaxis requiring hospitalization).
2. Subjects with a history of or a current immunosuppressive condition (*e.g.*, human immunodeficiency virus [HIV] infection).
3. Subjects with a history of malignancy within the past 5 years (except for carcinoma *in situ* of the uterine cervix, basal cell carcinoma of the skin that has been treated with no evidence of recurrence, and prostate cancer medically managed through active surveillance or watchful waiting).

4. Subjects with clinically significant abnormalities detected on ECG regarding either rhythm or conduction (e.g., QT interval corrected for heart rate using Fridericia's formula [$QTcF] \geq 450$ ms, or a known long QT syndrome).
Note: A first degree heart block will not be considered as a significant abnormality.
5. Subjects with acute IPF exacerbation within 6 weeks prior to screening and during the screening period.
6. Subject with a lower respiratory tract infection requiring antibiotics within 4 weeks prior to screening and during the screening period.
7. Subjects who have been smoking within 3 months prior to screening.
8. Interstitial lung disease (ILD) associated with known primary diseases (e.g., sarcoidosis, amyloidosis, etc.), exposures (e.g., radiation, silica, asbestos, coal dust, etc.), and drugs (e.g., amiodarone, etc.).
9. Subjects with a history of lung volume reduction surgery or lung transplant.
10. Subjects with an unstable cardiac or pulmonary disease (other than IPF) within 6 months prior to screening or during the screening period, including but not limited to:
 - a. unstable angina pectoris, myocardial infarction
 - b. congestive heart failure requiring hospitalization
11. Subjects with any clinical condition or circumstance that in the opinion of the investigator may make a subject unsuitable for inclusion or unable to complete the study or comply with study procedures and requirements.
12. Subjects with a contra-indication for bronchoscopy and bronchoalveolar lavage in the opinion of the investigator.
13. Subjects with an abnormal liver function defined as aspartate aminotransferase (AST), alanine aminotransferase (ALT), or bilirubin >3 x upper limit of the normal range (ULN).

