14. Subjects with an abnormal renal function defined as creatinine clearance < 50 mL/min using the Cockcroft-Gault equation.
15. Subjects participating in a drug/device or biologic investigational research study (concurrently with the current study or within 8 weeks prior to screening).
16. Subjects using of any of the following therapies within 4 weeks before screening:
 - a. Pirfenidone
 - b. Nintedanib
 - c. Warfarin
 - d. Imatinib
 - e. Ambrisentan
 - f. Azathioprine
 - g. Cyclophosphamide
 - h. Cyclosporine A
 - i. Prednisone at steady dose > 15 mg/day (for details, see Section 4.2.4)
 - j. Any experimental IPF therapy
17. Subjects with active alcohol or substance abuse in the opinion of the investigator.

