5.4.2. Clinical Laboratory Evaluations

Blood samples of approximately 16 mL (or approximately 21 mL at screening only) will be collected predose by venipuncture (or indwelling catheter for pharmacokinetic sampling days) in the arm at the time points indicated in the study flow chart (provided in Section 1) and according to sequence of study assessments as described in Section 5.1. In addition, urine samples for the clinical laboratory assessments will be collected. Subjects do not need to be fasted at the time of sampling.

Blood and urine samples will be collected for the following clinical laboratory tests:

- hematology: hematocrit, hemoglobin, red blood cell count, WBC total count, WBC differential count (absolute and relative), and platelets
- serum/plasma chemistry: glucose, urea, creatinine, uric acid, sodium, potassium, calcium, chloride, phosphorus, AST, ALT, gamma glutamyl transferase, total bilirubin, alkaline phosphatase, albumin, total proteins, triglycerides, cholesterol, and brain natriuretic peptide
- coagulation parameters: international normalized ratio and partial thromboplastin time
- urinalysis: pH, glucose, proteins (quantitative); ketones, and microscopic examination of the sediment (cylinders, erythrocytes, leucocytes)
- serology: hepatitis B surface antigen, hepatitis B virus antibody, HIV-1 and HIV-2 antibody (only at screening)
- FSH (only at screening in case there is doubt on whether a female subject is postmenopausal)

The laboratory values outside the normal range will be flagged and clinical relevance will be assessed by the investigator. More frequent sampling as well as additional tests may be performed as deemed necessary by the investigator to follow-up and resolve any safety concerns.

Note that in case clinically significant laboratory test results are a potential reason for discontinuation from the study drug and withdrawal from the study, retesting should be prompt (within 3 to 5 days) after the investigator has consulted with the medical monitor. A decision regarding subject discontinuation should be made only after the results from the retest are available (see Section 4.2.5 for additional information).

The details of sample handling and shipment instructions will be provided in a separate laboratory manual.

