5.4.4. Physical Examination

The physician (or a trained assistant or nurse practitioner, as applicable by local regulations) will perform a full physical examination (including ear, nose, throat, neck, chest, abdomen, and extremities) predose at the time points indicated in the study flow chart (provided in Section 1) and according to sequence of study assessments as described in Section 5.1.

Height and weight will be measured at screening only (with shoes off).

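### The Child-Pugh B or C limit in Section 2.5 is only partly carried into the eligibility criteria: exclusion 13 tests AST, ALT and bilirubin, and the rest is left to investigator judgement

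*Protocol*

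**What the plan says.** Section 2.5 (Clinical Risks/Benefits) gives its reason first, "As there is limited clinical experience with GLPG1690 so far", and then says the drug "should not be administered to subjects with moderate to severe renal impairment, hepatic impairment (Child-Pugh B or Child-Pugh C), or pediatric subjects".

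Section 4.1 describes subjects being "screened to determine eligibility as per the inclusion and exclusion criteria" and points to Sections 4.2.2 and 4.2.3. In those sections:

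- **Renal:** exclusion 14 removes "Subjects with an abnormal renal function defined as creatinine clearance < 50 mL/min using the Cockcroft-Gault equation".
- **Paediatric:** inclusion 2 requires age 40 years or over.
- **Hepatic:** exclusion 13 removes "Subjects with an abnormal liver function defined as aspartate aminotransferase (AST), alanine aminotransferase (ALT), or bilirubin" above 3 x ULN.

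Two general clauses could also apply. Inclusion 8 opens "Subjects must be in a stable condition and acceptable for study participation" and rests on history, examination, vital signs, ECG and laboratory results. Exclusion 11 covers any condition that the investigator thinks makes a subject unsuitable.

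The laboratory panel in Section 5.4.2 includes total bilirubin, albumin and "coagulation parameters: international normalized ratio and partial thromboplastin time", and the flow chart schedules it at screening.

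**The concern.** One sentence in the protocol names three groups who should not be dosed. A site that works through the eligibility list meets a fixed rule for two of them. For the third it meets a liver criterion built on different quantities. Child-Pugh class does not appear in Sections 4.2.2, 4.2.3 or 4.2.4, and no criterion there names cirrhosis, ascites, encephalopathy, albumin or INR.

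What is at stake is subject protection. A safety limit that the protocol itself states is enforced partly by rule and partly by each investigator's judgement, so sites could apply it differently. Clinical experience at this point, per Section 2.4, is 40 healthy men given drug or placebo.

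**Working it through.** The protocol gives no figure to reproduce. The check compares the Section 2.5 limits with the criteria, then asks whether passing exclusion 13 rules out Child-Pugh B or C.

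**Step 1. Match each limit to a criterion.**

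| Limit in Section 2.5 | Criterion | Carried over? |
|---|---|---|
| Moderate to severe renal impairment | Exclusion 14: creatinine clearance < 50 mL/min | Yes, fixed rule |
| Paediatric | Inclusion 2: age ≥ 40 years | Yes, fixed rule |
| Child-Pugh B or C | Exclusion 13: AST, ALT or bilirubin > 3 x ULN | Partly |

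**Step 2. Assumption.** The protocol does not define Child-Pugh scoring. The standard scheme is assumed: five items (bilirubin, albumin, INR, ascites, encephalopathy), each scored 1 to 3, with A = 5–6, B = 7–9 and C = 10–15. AST and ALT are not items, so bilirubin is the only overlap with exclusion 13.

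**Step 3. Range with bilirubin at its lowest score (1 point).**

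- Minimum: 1 + 4 × 1 = 5 (class A)
- Maximum: 1 + 4 × 3 = 13 (class C)

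All three classes remain possible even when AST, ALT and bilirubin are normal.

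**Step 4. Count of patterns.** The other four items have 3⁴ = 81 score patterns.

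- A total of 7 or more needs those four to sum to at least 6. Only 1 pattern sums to 4 and 4 patterns sum to 5, so 81 − 5 = 76 patterns give class B or C.
- A total of 10 or more needs a sum of at least 9. Sums of 9, 10, 11 and 12 arise in 16, 10, 4 and 1 patterns, so 31 give class C.

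These count what is possible. They are not prevalences.

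**Step 5. A more conservative case.** Suppose the consent and comprehension requirements (inclusions 1 and 11) rule out encephalopathy, and ascites would always be noticed. Bilirubin, encephalopathy and ascites then score 1 each, leaving albumin and INR.

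- Minimum: 3 + 2 × 1 = 5 (class A)
- Maximum: 3 + 2 × 3 = 9 (class B)

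Class B can still be reached on two laboratory results that are drawn at screening but have no eligibility limit.

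**The case against.** The strongest reply is that the limit is already in the protocol. Section 10.1 requires the study drug to be handled strictly in accordance with the protocol, so an investigator applying exclusion 11 has Section 2.5 as an express standard. What is missing would then be a cross-reference more than a safeguard.

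Several other clauses also bear on the point:

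- Inclusion 8 is mandatory and draws on most of the information a Child-Pugh assessment would use.
- Inclusion 9 requires a life expectancy of at least 12 months.
- Inclusions 1 and 11 require the capacity to consent and to understand the study.
- Exclusion 12 covers contra-indications to bronchoscopy, where a deranged INR would be weighed.
- Exclusion 17 covers active alcohol abuse.

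The renal comparison can be challenged too: the protocol never defines moderate impairment, so exclusion 14 is also a laboratory cut-off standing in for a clinical category. Finally, the hepatic limit rests on limited experience and not on an identified hazard. Laboratory tests at every visit, the liver withdrawal rules in Section 4.2.5 and the independent safety review in Section 7 would limit harm.

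Much of this stands as an argument about likelihood. Overt decompensation would probably be refused. But none of these clauses names the hepatic limit or sets a threshold for it, and Section 2.5 is background text while Section 4.1 sends sites to 4.2.2 and 4.2.3. The on-study protections act after dosing has begun. As to the renal comparison, exclusion 14 may not match its category exactly, but it does set a cut-off on kidney function. Two of the three tests in exclusion 13 are not part of the scale that Section 2.5 uses.

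**Conclusion.** The point holds. Exclusion 13 only partly implements the hepatic limit in Section 2.5. For a subject within its AST, ALT and bilirubin limits, only judgement clauses stand between Child-Pugh B or C and randomisation.

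The size is modest. Two of the three limits have a matching fixed criterion and the third is partly covered through bilirubin. The frequency of affected subjects cannot be derived from the protocol and is probably low with about 24 subjects planned. The finding makes no claim of an effect on PK or on any analysis.

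The conclusion that the two are not equivalent rests on standard Child-Pugh scoring, which is assumed. The absence of Child-Pugh from the criteria can be read directly from the text. The change should be made because the criteria as written could admit subjects whom the protocol says not to dose, and closing the gap costs little.

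**What to change.** Add one exclusion to Section 4.2.3 and keep exclusion 13 unchanged. Suggested text: *Known or suspected hepatic impairment of Child-Pugh class B or C, assessed from screening total bilirubin, albumin and INR, and from ascites and encephalopathy on history and examination.*

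The cost is one line of protocol text and no new blood test, since all three laboratory items are already in the screening panel. The examination in Section 5.4.4 already covers the abdomen but lists no mental-status assessment, so encephalopathy would have to be asked about or briefly checked.

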2.6. RATIONALE FOR THE STUDY

Recent literature has suggested a role for ATX, an enzyme with lysophospholipase D activity responsible for the production of LPA, in disease-affected lung function. Interventions targeting the ATX/LPA pathway could lead to a new class of therapy for IPF.

GLPG1690 is the first ATX inhibitor in clinical development for the oral treatment of IPF. Preclinical studies suggested a high level of target engagement (21-day BLM mouse models): after GLPG1690 treatment, the increase of LPA levels in BALF after BLM exposure was reduced for several LPA species. Moreover, GLPG1690 provided similar or better results than pirfenidone - in the same model - in terms of the reduction in lung weight and Ashcroft score and prevention of collagen deposit in the lung. In addition, GLPG1690 dose-dependently inhibited the production of CTGF upon TGF β -triggering in normal human dermal fibroblasts.

Results from a FIH study generated promising PD results (LPA reduction) and indicated the study drug was generally safe and well tolerated in a population of healthy subjects.

As a next step in the clinical development of GLPG1690, its safety, tolerability, PK, and PD properties will be evaluated in this Phase IIa study in subjects with IPF.

Rationale for the Study Design

This is a randomized, double-blind, parallel group, placebo-controlled, multicenter, exploratory Phase IIa study including subjects with IPF. The randomized double-blind study design was chosen as it is the most rigorous method to generate high quality scientific data. In addition, a placebo-controlled study contains internal evidence of assay sensitivity (*i.e.*, when a difference is demonstrated, it is interpretable without reference to external findings), measures absolute safety and efficacy (*i.e.*, it measures the total pharmacologically mediated effect of treatment), is very efficient (*i.e.*, can measure treatment effects with a smaller sample size compared with any other type of controlled study), and minimizes the effect of subject and investigator expectations (ICH E10, 2000).

The subject eligibility criteria are typical for patient studies in IPF. Since the disease typically affects elderly subjects, it was chosen to include subjects aged ≥ 40 years. Subjects could neither use the 2 drugs approved for the treatment of IPF (*i.e.*, pirfenidone and nintedanib) nor warfarin, imatinib, ambrisentan, azathioprine, cyclophosphamide, cyclosporine A, prednisone at steady dose > 15 mg/day, and any other experimental IPF therapy within 4 weeks prior to screening and during the study in order to avoid any confounding effects these drugs may have on the safety, tolerability, PK, PD, or exploratory endpoints evaluated in the current study.

The treatment duration of 12 weeks was chosen as currently, the preclinical safety of the drug has been evaluated up to a maximum of 13 weeks treatment duration.

Rationale for the Outcome Measures

Safety and tolerability will be assessed by the evaluation of adverse events (AEs), selected clinical laboratory parameters, vital signs, physical examinations, and ECG, all of which are standard safety evaluations in clinical development.

The PK assessments are included since the PK profile in IPF patients may differ from that of healthy subjects included in the FIH study. Information obtained on the PK of GLPG1690 will guide dose selection in future clinical studies.

The PD properties of GLPG1690 will be assessed through the analysis of plasma LPA, a PD biomarker of ATX inhibition. The effect of GLPG1690 on LPA in plasma has been confirmed

in the FIH study, where GLPG1690 reduced LPA levels in a dose-dependent way. The current PD analysis will confirm the effect in a population of IPF patients.

In addition, effects of GLPG1690 on different LPA species will be assessed pre- and post-treatment in the BALF, representative for target engagement in a matrix closer to the lung. Such data were already generated in the mouse BLM model: several LPA species increased in the BALF after BLM inhalation and were reduced again after GLPG1690 treatment. These data correlated with a positive effect of GLPG1690 on a series of fibrotic readouts (lung weight, Ashcroft score, collagen deposit in lung).

Pulmonary function will be assessed using standard spirometry; FVC is currently the most commonly used and accepted endpoint in clinical studies investigating IPF treatments (Saketkoo, et al., 2014). Spirometry, or more specifically FVC reflects the burden of the IPF progress, and is relatively easy to measure and reproducible (Nathan & Meyer, 2014). However, since conventional pulmonary function tests such as spirometry have their limitations (*e.g.*, they cannot detect early signs of disease due to the compensatory behavior of healthy lung areas; in IPF, many spirometry endpoints remain normal even though the disease progresses) and since a study duration of 12 weeks may be considered too short to detect any differences in FVC, pulmonary function will also be assessed through high-resolution computed tomography (HRCT) scans used for generating functional respiratory imaging (FRI). FRI provides regional information about lung structure and allows for earlier demonstration of disease progression and/or therapeutic effects (De Backer, et al., 2015; Vos, et al., 2015). Furthermore, central reading of these images should reduce assessment bias.

In addition, change in the levels of a selection of biomarkers in blood and BALF (through bronchoscopy) will be assessed. Even though there currently are no validated biomarkers that track IPF progression or response to IPF treatment, a number of protein biomarkers have been shown to be increased in IPF (*e.g.*, ATX, Krebs von den Lungen 6/mucin type 1 [KL-6/Muc1], surfactant protein A (SP-A), chemokine motif ligand 18 [CCL18], surfactant protein D (SP-D), matrix metalloproteinase (MMP) 1, MMP7, intercellular adhesion molecule type 1 (ICAM1), vascular cell adhesion molecule type 1 (VCAM1), interleukin 8 (IL8), and S100 calcium-binding protein A12 (S100A12) (Greene, et al., 2002; Rosas, et al., 2008; Hara, et al., 2012; Kaminski, et al., 2012; Oikonomou, et al., 2012; Richards, et al., 2012; Jenkins & Goodwin, 2014; Nathan & Meyer, 2014) (Jenkins, et al., 2015). Change in a selection of biomarkers of disease activity will be evaluated in the current study. Results will help to refine our current understanding of the effect of GLPG1690 on IPF pathophysiology and will guide endpoint selection in future clinical studies.

Finally, since IPF is a chronic, severely debilitating, and ultimately lethal disease, any treatment should aim to improve subject's quality of life; therefore, patient-reported outcomes are important parameters in any study in IPF. The St. George's Respiratory Questionnaire (SGRQ), a quality of life measurement tool, was selected for the current study (Nathan & Meyer, 2014; Swirgis, Esser, Conoscenti, & Brown, 2014).

Information on the rationale for dose selection is provided in Section 2.7.

